4.2.3.5 Analysis and Inference of the Primary Endpoint

The treatment effect on the primary endpoint is estimated using an analysis of covariance (ANCOVA) with response variable change in MG-ADL from baseline to Week 24 adjusting for treatment group and the same covariates as for the imputation model.

The primary treatment effect estimate is the regression coefficient of the treatment group.

The estimate of variance coming from the ANCOVA will underestimate the true variance as it ignores the variance due to the imputation. To correct the underestimation of the variance the jackknife is applied to all previous steps (2-3) of the imputation modeling, that is an imputation model is fit on each data set with one participant removed. The p-value of the treatment effect is derived through the Wald test.

4.2.4 Sensitivity Analyses for Primary Endpoints

The robustness of the primary method of estimation will be explored using a series of sensitivity and supplementary estimators based on varying different aspects of the primary endpoint, including sensitivity analyses exploring robustness of departures from statistical assumptions and supplementary analyses investigating the trial data as listed in this section. The p-values from sensitivity and supplementary analyses of the primary endpoint are for descriptive purpose only, and there will be no multiplicity adjustment for these analyses.

We propose a series of sensitivity analyses to further assess the potential dependence of the results of the primary analysis on missing values. However, additional sensitivity analyses may be considered if appropriate.

4.2.4.1 Impact of Rescue Therapy

To assess the impact of rescue therapy in AChR+ participants all values after the administration of rescue therapy are replaced by the worst possible MG-ADL assessment that a particular participant has had prior to receiving rescue therapy. This

imputation overwrites the estimand specified imputation strategy. The impact will be estimated using an MMRM.

4.2.4.2 Impact of Major Protocol Deviations

To assess the impact of major protocol deviations, the primary analysis will be run excluding participants with a major protocol deviation of which an impact on the efficacy outcome is expected. A separate analysis for each type of major protocol deviation is conducted:

- 1. Violation of the inclusion criteria of the MG-ADL score at screening
- MG-ADL not performed in the order specified per protocol at DB Week 0 and/or Week 24
- MG-ADL assessment performed by non-qualified site personnel at DB Week 0 and/or Week 24
- 4. Failure to maintain dual assessor approach.

4.2.4.3 Tipping Point Analysis

A δ tipping point analysis will be conducted on all participants who discontinue satralizumab treatment. The MG-ADL value after stopping treatment will be replaced by the last available assessment prior to stopping plus an additive constant delta. The treatment effect will be re estimated for varying values of delta $(0,\infty)$ until the first delta at which the primary analysis treatment effect p-value will exceed 5%. The minimal value of delta at which this happens is referred to as the tipping point. This imputation will overwrite the estimand specified imputation strategy.

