#### 3.1.6 Safety Follow-Up

Patients who discontinue study treatment during the DB period for any reason should continue with the remaining assessments defined in the protocol. All efforts will be made to minimize missing data. However, patients who are unwilling to return to the clinic for all assessments will be asked to complete an end of treatment (EOT) visit within 4 weeks and a safety follow-up (SFU) visit 12 weeks after the final dose of study drug.

Patients who discontinue study treatment during the OLE period will be asked to complete *an* EOT visit *within* 4 weeks and *a* SFU visit 12 weeks after the final dose of study drug. Patients who decide to continue treatment with satralizumab outside of this study will have to complete the EOT visit, but they will not have to complete the SFU or end of study visit.

For patients aged  $\geq$  12 to < 18 years at the time of informed consent, who withdraw from the study or complete the extension period, an additional follow-up assessment will be conducted at 24 weeks after the final dose of study drug.

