## 6.4.2 Primary Efficacy Estimator

The primary efficacy analyses will compare satralizumab with placebo at Week 24 in the AChR+population.

The following null and alternative hypotheses will be tested at a two-sided significance level:

H0: μsatralizumab = μplacebo Versus H1: μsatralizumab ≠ μplacebo

for which  $\mu_{\text{satralizumab}}$  and  $\mu_{\text{placebo}}$  refer to the mean change from baseline to Week 24 in the total MG-ADL score in the satralizumab and placebo groups respectively. The primary efficacy objective is to evaluate the efficacy of satralizumab versus placebo on daily function. Patients will be grouped according to the treatment assigned at randomization.

An estimate of the treatment effect will be computed using a "Mixed Model Repeated Measures" analysis adjusting for the randomization stratification factors (background therapy, autoantibody type, and region) and baseline MG-ADL score.

For NSDCR withdrawals, data will be censored at the time of the treatment withdrawal. Any data collected after NSDCR withdrawal will be disregarded. Missing data following a withdrawal that is determined to be NSDCR will be imputed using multiple imputation with a "Missing at Random" assumption.

Missing data following a withdrawal that is determined to be SDCR will be imputed using reference based multiple imputation with a "Copy Reference" assumption. This approach will only be used if observed data following a treatment withdrawal are not available. Where observed data are available, they will continue to be included in the analysis.

Data following rescue therapy and treatment interruption due to infection will be included in the analysis. Approaches to handle item level missing data will be described in the SAP.

The robustness of the primary estimation method will be explored by a series of sensitivity estimators based on varying assumptions underlying the multiple imputation strategy and classification of treatment withdrawal intercurrent events as SDCR or NSDCR. Additional details will be provided in the SAP.

Patients who discontinue from the study treatment for any reason should continue with all remaining assessments defined during the DB period of the protocol. However, patients who are unwilling to return to the clinic for all assessments will be asked to complete the EOT within 4 weeks and *a* SFU visit 12 weeks *after* the final dose of study drug.

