Official Title: A Phase III, Randomized, Double-Blind, Placebo-Controlled,

Multicenter Study to Evaluate Efficacy, Safety, Pharmacokinetics, and

Pharmacodynamics of Satralizumab in Patients with Generalized

Myasthenia Gravis

NCT Number: NCT04963270

Document Date: Statistical Analysis Plan Version 3: 16-Jan-2024

STATISTICAL ANALYSIS PLAN

STUDY TITLE: A PHASE III, RANDOMIZED, DOUBLE-BLIND,

PLACEBO-CONTROLLED, MULTICENTER STUDY

TO EVALUATE EFFICACY, SAFETY,

PHARMACOKINETICS, AND

PHARMACODYNAMICS OF SATRALIZUMAB IN PATIENTS WITH GENERALIZED MYASTHENIA

GRAVIS

STUDY NUMBER: WN42636

STUDY NAME: Luminesce

VERSION NUMBER: 3

ROCHE COMPOUND(S): Satralizumab (RO5333787)

EUDRACT NUMBER: 2020-004436-21

IND NUMBER: 151937

NCT NUMBER: NCT04963270

PLAN PREPARED BY: , Ph.D

STATISTICAL ANALYSIS PLAN APPROVAL

SPONSOR: F. Hoffmann-La Roche Ltd [name]

DATE FINAL: See electronic date stamp on the last page of this

document

CONFIDENTIAL

This is an F. Hoffmann-La Roche Ltd document that contains confidential information. Nothing herein is to be disclosed without written consent from F. Hoffmann-La Roche Ltd.

Satralizumab—F. Hoffmann-La Roche Ltd Statistical Analysis Plan WN42636

STATISTICAL ANALYSIS PLAN VERSION HISTORY

This Statistical Analysis Plan (SAP) was developed based on Roche SAP model document 28 February 2022.

SAP Version	Approval Date	Based on Protocol (Version, Approval Date)
2	See electronic date stamp below	Protocol version 5, dated 19 July 2023
1	30 May 2023	Protocol version 3, dated 10 Nov 2021

STATISTICAL ANALYSIS PLAN AMENDMENT RATIONALE VERSION 3

Key changes to the SAP, along with the rationale for each change, are summarized below.

Section	Description of Change	Rationale for Change
4.2 Primary Endpoint Analysis	Pooling of North America and Europe for stratification by Region	Low number of participants from North America
4.2.3.1 Missingness of covariate data	Removed section	Does not apply to the collected data set
4.2.4 Sensitivity Analyses for Primary Endpoints	Removal of Sections: Impact of Imputations on Item Level, Impact of Imputation Modeling Approach, Impact of Outliers	Sections are not needed and have been replaced by FDA Requested Tipping Point Analysis
4.2.5 Supplementary Analyses for Primary Endpoint	Rephrased subgroup analyses and removed subgrouping by type of rescue therapy	Low number of rescue therapy administration

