Data Collection	Regardless of ICE occurrence, the participant will be ask endpoint and data collection will continue as long as poss	ed to remain in the study to be evaluated for the primary efficacy sible.
Data Strategy	Data are used as available to estimate a treatment effect irrespective of the occurrence of SDCR ICE. This assumption will estimate the treatment effect by analyzing outcomes as they were observed, assuming rescue therapy is part of the standard treatment regimen and hence data are considered as recorded.	All data after an ICE is ignored.

Table 5 Handling of ICEs for the Primary Endpoint

Intercurrent Event Classification	Study Drug or Condition Related (SDCR)	Not Study Drug or Condition Related (NSDCR)
Imputation Strategy	If data are unavailable, or only partial data are available subsequent to a SDCR ICE, then data are used as available and the remainder is imputed using copy reference. Data are imputed using copy reference methodology (i.e., data are imputed from the placebo arm). The underlying assumption being that participants who discontinue the active arm did not get a benefit from the proposed treatment after the SDCR ICE. In other words, the participant profile following SDCR ICE tracks that of the reference arm but starting from the benefit already obtained.	Data are imputed using a missing at random assumption that is data will be imputed conditional on observed data. The imputation under a missing at random assumption estimates a treatment effect as if the ICE had not happened.

¹ For the generic ICE "Withdrawal from study treatment" information on the cause and categorization into whether the interruption is study drug or condition related (SDCR) or not SDCR (NSDCR) is collected in the electronic Case Report Form.

If a participant has recorded multiple ICEs, then the category of the first ICE will determine the handling strategy of all subsequent missing data.

² Receiving rescue therapy might not result in a treatment interruption but is a relevant ICE in this study that always falls under the SDCR category.

 $^{^{\}rm 3}$ Treatment interruption due to infection will always be categorized as SDCR.

The precise statistical imputation methodology is detailed in section on missingness and imputation.

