4.2.3.4 Imputation Due to Intercurrent Events

In the following we describe missingness and data imputation due to IECs. A detailed statistical justification for this imputation strategy can be found in Wolbers M et al. (2021).

- 1. For each participant the time of the first ICE is determined using the ICE data set. For each efficacy score a data set is created where all subsequent data to the first ICE is removed. If a participant has multiple ICEs between which normal dosing of study drug is attained all the data are nevertheless removed in a first step, i.e., data that would be dealt under treatment policy is still removed in this step. This ensures that the imputation model is fitted on data that is completely unaffected by ICEs.
- 2. A mixed model repeated measures (MMRM) model is fitted as an imputation model to address all the missingness due to ICEs. The MMRM is modeling change from baseline of the efficacy score (separate MMRMs will be fitted for each score) and has the following covariates: treatment group, visit, treatment group x visit, baseline stratification factors (background therapy, auto-antibody type [where this applies], region), baseline efficacy score and baseline efficacy score x visit. ("x" refers to complete interactions). The MMRM will use an unstructured covariance overall, in case of convergence issues the covariance structure will be simplified to compound symmetry. The resulting model will serve as a model for all imputations of longitudinal data in the next step.

3. The MMRM model implies a multivariate normal imputation distribution conditional on baseline covariates and conditional on observed longitudinal data that is not affected by an ICE. The implied conditional mean of this normal distribution is used to impute missing data. Participants with an ICE but subsequent data available which falls under treatment policy will use the observed data and will not be imputed. Participants on the satralizumab arm with missing data due to an ICE in category SDCR will be imputed using the imputation model and their treatment group covariate will be artificially set to placebo (copy reference imputation), this way their data are imputed as if they had not had a benefit from the treatment after the ICE. This imputation procedure will result in a complete data set for each efficacy score. All the efficacy analyses will be conducted on the completed data sets.

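### The tipping-point delta starts from the last score before stopping and, as worded, also overwrites observed scores, so it is not distance from the primary result

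*SAP*

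**What the plan says.** **The tipping-point run.** SAP 4.2.4.3 covers every participant who discontinues satralizumab. Its rule is: "The MG-ADL value after stopping treatment will be replaced by the last available assessment prior to stopping plus an additive constant delta". It adds: "This imputation will overwrite the estimand specified imputation strategy". Delta is raised over (0, ∞) until the p-value passes 5%. The SAP version 3 amendment table gives the origin of the run and says which imputation checks it displaced: "Sections are not needed and have been replaced by FDA Requested Tipping Point Analysis".

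**The primary analysis.** After an SDCR event, SAP Table 5 says "data are used as available and the remainder is imputed using copy reference". SAP 4.2.3.4 confirms it: "Participants with an ICE but subsequent data available which falls under treatment policy will use the observed data and will not be imputed". Protocol 6.4.2 agrees for SDCR withdrawals: "Where observed data are available, they will continue to be included in the analysis". NSDCR withdrawals are handled differently: "Any data collected after NSDCR withdrawal will be disregarded" and the gap is imputed as missing at random.

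**Observed post-stopping scores are expected.** Protocol 3.1.6 says: "Patients who discontinue study treatment during the DB period for any reason should continue with the remaining assessments defined in the protocol".

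**Aim and commitments.** SAP 4.2.4 presents its sensitivity analyses as a check on how far the primary result rests on missing values. Protocol 6.4.2 also commits to varying the SDCR/NSDCR classification of withdrawals. SAP 4.2.4 and 4.2.5 contain no such run. SAP section 1 gives the SAP precedence over the protocol for filings, and SAP Appendix 1 does not record the check as dropped.

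**The concern.** A tipping delta is normally read as how much worse the unobserved outcomes would have to be, relative to what the primary analysis assumed, before significance is lost. SAP 4.2.4.3 does not deliver that, for two reasons.

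- **Scope.** The rule is not limited to missing values, and it overrides the estimand's handling. Taken literally, it replaces scores that were observed after SDCR withdrawal and that the primary analysis uses. A tip found this way reflects both the missing-data assumption and the loss of real treatment-policy data.
- **Anchor.** Even if only missing scores are replaced, delta = 0 is LOCF. It is neither copy reference nor missing at random, so delta = 0 does not return the primary result. The same fragility is reported as a smaller or larger delta depending on who stops and when.

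What is at stake is how the robustness statement is read. The primary estimate does not change. The run matters because it replaced other imputation checks and is the main one left for missing data after withdrawal.

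**Working it through.** **1. Planning figure.** SAP 2.2 gives changes of 2.3 (placebo) and 4.3 (satralizumab), SD 3.97, two-sided 0.05, 85% power and 10% withdrawal. The normal formula gives 71 per arm, or 79 after dividing by 0.9 (158 in total). The t-based version gives 72 per arm, and 72/0.9 = 80 (160 in total). The stated 160 reproduces.

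**2. Scale.** SE = 3.97 × √(2/80) = 0.628. Critical difference = 1.96 × 0.628 = 1.23. Ten percent of 80 is 8 satralizumab discontinuers.

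**3. Where delta = 0 sits.** The documents do not give the correlation between the stopping visit and Week 24. Assume 0.5, equal SDs and, for this step only, flat mean profiles. Copy reference is then −2.3 + 0.5 × (last change + 2.3), and missing at random is −4.3 + 0.5 × (last change + 4.3).

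| Last change | Copy reference | LOCF minus copy reference | Missing at random | LOCF minus missing at random |
|---|---|---|---|---|
| −4.3 | −3.30 | −1.00 | −4.30 | 0.00 |
| −2.3 | −2.30 | 0.00 | −3.30 | +1.00 |
| 0 | −1.15 | +1.15 | −2.15 | +2.15 |

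The offset from copy reference changes sign with the participant's response. With correlation 0.3 to 0.7 it runs from −1.4 to −0.6 in the first row and from +1.6 to +0.7 in the last.

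**4. Closed form for a delta added to primary-imputed scores.** With a fraction f of the arm shifted, solve (2.0 − f·d) / √[(3.97² + f(1−f)d²)/80 + 3.97²/80] = 1.96. With 8 of 80 shifted, d = 6.9. With 4 of 80 shifted, d = 12.6. So the number of scores the run is allowed to move nearly doubles or halves the answer. That is why it matters whether observed scores are replaced.

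**5. Simulation.** Set-up: 80 per arm; 8 satralizumab discontinuers stopping at Week 12; correlation 0.5; means building up exponentially (6-week constant) to −4.3 and −2.3; copy-reference conditional means; difference in means instead of ANCOVA; trials kept if the primary effect is within 0.1 of 2.0; no limit on scores. Timing, response and the number still observed are assumptions.

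*No discontinuer observed, so both readings coincide:*

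| Who stops | Delta as worded | Delta from the primary imputation | Mean imputed Week 24 change at the tip (as worded v primary) |
|---|---|---|---|
| Worst 30% | 4.8 | 6.4 | 5.6 v 5.6 |
| Average | 7.1 | 6.7 | 3.7 v 3.8 |
| Best 30% | 10.3 | 7.3 | 1.8 v 1.8 |

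The two anchors tip at nearly the same imputed outcome, but the deltas that label it differ. Using a jackknife SE gives 4.7 v 6.6, 7.2 v 7.2 and 10.4 v 7.9, the same pattern. In those runs the effect at delta = 0 is 1.84, 2.06 and 2.30 against a primary of 2.0. With correlation 0.3 to 0.7 the worst-30% case gives 4.4 to 5.1 v 6.4 to 6.9, and the best-30% case 9.2 to 11.4 v 7.3 to 7.8. Missing at random at Week 12 gives 3.9 v 6.4, 6.3 v 6.8 and 9.4 v 7.3.

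*Four of 8 observed (jackknife SE):*

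| Who stops | Replace all | Replace missing only | Primary-anchored |
|---|---|---|---|
| Worst 30% | 4.5 | 9.8 | 11.7 |
| Average | 7.4 | 12.8 | 12.6 |
| Best 30% | 10.6 | 16.3 | 13.7 |

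A repeat of the worst-30% case gives 4.4 for replace-all against 11.5 for the primary-anchored run.

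**6. A borderline result.** Ignoring the growth in SE, an effect of 1.30 has (1.30 − 1.23)/0.10 = 0.7 points to the tip. If LOCF lies 1.0 better than copy reference, the reported delta is 1.7. If it lies 1.15 worse, 0.7 − 1.15 is negative, so the result has already tipped at delta = 0, outside the stated search range.

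**7. Reclassification.** Moving one average missing participant from NSDCR to SDCR changes the effect by (4.3 − |copy-reference value|)/80. That is 0.0096 to 0.0213 over correlations 0.3 to 0.7 and stopping at Week 4 or 12. Times 8, it is 0.077 to 0.170. It could alter significance only for a primary effect between 1.23 and 1.23 + 0.17 = 1.40.

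**The case against.** The best defence is that, when only missing scores are replaced, the SAP run does what a tipping-point analysis should. It worsens the unobserved outcomes until significance fails, and it fails at almost the same mean imputed score as a primary-anchored run. Points worse than at stopping is an interpretable scale, and the SAP never says delta is distance from the primary assumption. This stands. A reader might infer that the run is invalid or says nothing about missing data. On the missing-only reading the documents do not support that; the gap is one of labelling and of delta = 0 not matching the primary. The defence does not cover the literal wording, under which observed scores are lost.

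Other points also carry weight:

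- **FDA origin.** The request itself is not in the documents. Its form may have been agreed, so the run should not be removed.
- **Other runs.** It would be too strong to say that nothing else in the SAP varies copy reference. Rescue always counts as SDCR, and SAP 4.2.4.1 replaces all post-rescue values with the participant's worst earlier score. The gap concerns missing data linked to withdrawal and other missing data.
- **Size.** Average stoppers at Week 12 show little difference. The larger gaps need selective stopping, or the literal reading with observed scores. The figures are uncapped, and MG-ADL ends at 24, so deltas above 11 may not be reachable.
- **Reclassification.** The 0.17 maximum supposes that all 8 were investigator-classified NSDCR with missing data. SAP 4.2.1.2 fixes several reasons in advance, SAP 4.6.4 tabulates events by class, and SAP 4.2.4 allows further analyses. None of these pre-specifies the run.

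**Conclusion.** The concern holds in a limited form. On its literal wording, SAP 4.2.4.3 discards post-SDCR scores that the primary analysis keeps, and so mixes an estimand change with the missing-data question. Its tipping delta can then be far from one confined to missing data (about 4.4 against 11.5 in the illustrative worst case). If only missing scores are replaced, the run is valid, but its delta is measured from LOCF. It can make the same result look more fragile (4.8 against 6.4) or more robust (10.3 against 7.3). The sizes rest on assumed correlation, stopping time, selection of stoppers and number still observed, with no limit on scores.

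A reader might infer that the primary conclusion is in doubt. It is not: the primary estimate and type I error are untouched, and SAP 4.2.4 makes sensitivity p-values descriptive. The missing reclassification run is a minor, unrecorded departure from Protocol 6.4.2. Together these justify a cheap improvement, not a change to the main analysis.

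**What to change.** 1. Keep the FDA-requested run and state in SAP 4.2.4.3 whether scores observed after stopping are replaced.
2. Add one delta run that leaves untouched the observed scores the primary analysis uses. Add delta only to satralizumab Week 24 scores that the primary analysis imputed, and keep scores within 0 to 24. Delta = 0 is then the primary result.
3. For both runs, report the tipping delta and the mean imputed score at the tip. If the added run reaches the limit without tipping, say so.
4. Run the primary analysis once with every investigator-classified withdrawal set to SDCR, or record and justify in SAP Appendix 1 that this check was dropped.

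The cost is one SAP paragraph and two further runs of existing code. The downside is one more sensitivity result to report, and with the 0 to 24 limit it may not tip. The choice of anchor should be fixed before unblinding, because choosing it after seeing who stopped would weaken the robustness claim.
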